4.2.3.1 Subgroup analysis of the primary endpoint

Exploratory subgroup analyses of the primary composite endpoint will be performed for the characteristics listed in Table 1. A test of interaction between randomized treatment group and the subgroup variable will be performed in each Cox model, stratified by T2D and including as covariates history of hospitalization for HF, the relevant subgroup variable and the interaction between treatment and the subgroup variable. In addition to the number and percent of patients with event, event rate estimate, HR with 95% confidence interval and p-value for each subgroup, the interaction p-value will be presented. HRs with confidence interval will be presented in a forest plot, also including the event rate and interaction p-value. The p-values for the subgroup analyses and interaction will not be adjusted for multiple comparisons as the tests are exploratory and will be interpreted descriptively.

Table 1 Characteristics and categories for sub group analysis of the primary endpoint

Characteristic	Categories
Age (years)	<= 65, >65
Sex	Male, female
Race	White, Black or African, Asian, Other
Geographic region	Asia (China, India, Japan, Taiwan, Vietnam) Europe (Bulgaria, Czech Republic, Denmark, Germany, Hungary, Netherlands, Poland, Russia, Slovakia, Sweden, UK) North America (Canada, US) South America (Argentina, Brazil)
NYHA class at enrollment	II, III/IV
LVEF at enrollment	<= median, > median
NT-proBNP at enrollment	<= median, > median
Prior Hospitalization for HF	Yes, No
MRAs at baseline	Yes, No
Type 2 diabetes at baseline *	Yes, No
Atrial fibrillation or flutter at enrolment ECG	Yes, No
Etiology of HF	Ischemic, Non-ischemic/unknown
BMI (kg/m ²) at enrollment	<30, ≥30
Baseline eGFR (ml/min/1.73m ²)	<60, ≥60

* Defined as history of T2D or HbA1c ≥6.5% at both visit 1 and visit 2 (Section 4.1) The subgroup analysis by T2D status will exclude T2D as a stratification factor from the model.

The subgroup analyses will be repeated for the CV death component of the primary composite endpoint and the secondary composite endpoint of CV death or HF hospitalization.

No hazard ratio estimates with confidence interval and p-values will be given for subgroups with less than 15 events in total, both treatment groups combined.

4.2.3.2 Sensitivity analysis of the primary endpoint

Undetermined cause of death

A sensitivity analysis of the primary analysis where deaths adjudicated as ‘undetermined’ cause are not included as endpoint events, but treated as censoring events, will be performed.

Missing data and informative censoring

The time-to-event analysis using the Cox regression depends on the assumption of non-informative or ignorable censoring, corresponding to the missing-at-random assumption. The missing data in this context are patients who are prematurely censored due to WoC, LTFU or otherwise incomplete follow-up of endpoints. The amount of missing data will be described eg, in terms of the number of patients and patient time with incomplete follow-up as described in Section 4.1.5.

Patient retention and follow-up are at the forefront of study planning and conduct, and the amount of incomplete follow-up is expected to be small. To assess the impact of missing data and the robustness of the results with regard to the assumption of non-informative censoring, sensitivity analysis will be planned based on the evaluation of the missing follow-up and discussed in relation to the observed efficacy signal. This may include analysis where scenarios in terms of increased risk in censored patients are explored to identify a ‘tipping point’ where statistical significance would be lost.

4.2.4 Analysis of the secondary efficacy variables

The time-to-event secondary variables include

- time to the first occurrence of hospitalization for HF or CV death
- time to the first occurrence of any of the components of the renal composite endpoint
- time to death from any cause.

These endpoints will be analysed in the same manner as the primary variable, including stratification by T2D status at randomization. The composite of hospitalization for HF or CV death will be adjusted for history of hospitalization for heart failure. The renal composite endpoint will be adjusted for baseline eGFR. Censoring is described in Section 3.2 for each endpoint.

Additionally, exploratory subgroup analysis will be conducted for the secondary composite endpoint of CV death or HF hospitalization in the same way as the subgroup analysis for the primary endpoint.

4.2.4.1 Analysis of recurrent HF events and CV death

The composite outcome of recurrent HF hospitalizations or CV death will be analysed by the semi-parametric proportional rates model (Lin et al 2000) known as the LWYY (Lin-Wei-Yang-Ying) method, to test the treatment effect and to quantify the treatment difference in

terms of the rate ratio with 95% confidence interval and p-value. Recurrent HF hospitalizations, CV death and censoring processes all have continuous distributions so that HF hospitalization and death cannot happen at the same time. If a HF hospitalization and CV death occurred at the same day, then only CV death will be counted. Moreover, CV death is a terminating event which, unlike censoring, prevents the occurrence of new HF hospitalizations.

In addition, the two components in the composite endpoint (total HF hospitalizations and CV death) will be analysed separately to quantify the respective treatment effects and check the consistency between the composite and the components. For the analysis of total HF hospitalizations component, occurrence of CV death can be regarded as semi-competing risk (informative censoring) and may introduce a bias in the treatment effect estimate for HF hospitalizations (dilution of effect size if the drug has a positive effect on both components). In order to address this concern and to account for the correlation between the two components, the joint modelling (frailty model) approach (Rogers et al 2016) will be used for the component analyses.

For joint frailty analysis the following assumptions are made: (Liu et al 2004)

- As noted above, HF hospitalization and death cannot happen at the same day (only the CV death will be counted) and CV death is a terminating event which prevents the occurrence of new HF hospitalizations.
- The hazard function of CV death (the instantaneous risk of death given that the subject is still alive) follows a proportional hazards model with constant baseline hazard, stratified by T2D status at randomization with treatment and history of hospitalization for heart failure as covariates.
- The hazard function of recurrent HF hospitalizations (the instantaneous risk of having another HF hospitalization given that the subject is still alive) follows a proportional hazards model as well, with constant baseline hazard, stratified by T2D status at randomization with treatment and history of hospitalization for heart failure as covariates.
- Within subject recurrent HF hospitalizations and CV death are correlated events. This correlation varies from subject to subject. To account for this correlation, the hazard function of recurrent HF hospitalizations and hazard function of CV death are modeled by a joint a subject specific random frailty term which follows a gamma distribution with unit mean and unknown variance.
- Censoring (including non-CV death) is noninformative, in particular it does not depend on random frailty.

Estimation in the frailty proportional hazards model will be done using Gaussian quadrature approach (Liu and Huang 2008, Lu and Liu 2014, SAS Institute Inc. 2018). Since SAS PROC NLMIXED supports only normal distributions, a probability integral transformation to generate numbers from a gamma distribution will be used (Nelson et al 2006) following Liu and Huang 2008.

Additionally, non-parametric estimates of the marginal mean of the cumulative number of recurrent HF hospitalization rates over time will be calculated allowing for death as terminal event, and the estimates will be plotted (Ghosh and Lin 2000). The estimation will be done in SAS using the PROC PHREG and by treating the situation as competing risks with several records per subject (Andersen et al 2019)

4.2.4.2 Analysis of change from baseline at 8 months in the KCCQ total symptom score

Hypothesis testing

The composite rank-based endpoint representing the patients' vital status at 8 months and the change from baseline to 8 months in TSS in surviving patients, as defined in Section 3.2.3, will be analysed using the rank ANCOVA method (Stokes et al 2012) to test the null hypothesis of no differences in the distributions of ranked outcomes between the two treatment groups. Analysis will be stratified by T2D status at randomisation, and adjusted for the baseline TSS value as follows.

First the change from baseline to 8 months in TSS and vital status at 8 months, as well as values of the baseline TSS covariate will be transformed to standardized ranks, using fractional ranks and mean method for ties. Ranking for the composite endpoint will be done so that patients who died prior to the 8-month assessment are assigned the worst ranks within each stratum. Among the deceased the relative ranking will be based on their last value of change from baseline in TSS while alive before deriving fractional ranks. Then, separate regression models will be fit to the ranked data for each randomization stratum using a regression model for the ranked composite variable as dependent variable, adjusting for the ranked baseline covariate. Residuals from this regression model will be captured for further testing of differences between treatment groups. The Cochran-Mantel-Haenszel (CMH) test, stratified for the T2D status at randomization, using the values of the residuals as scores will be used to compare treatment groups.

Responses missing for reasons other than death will be imputed as described in section 'Handling of missing data'.

The p-value from the CMH test of treatment effect at 8 months will be used for the confirmatory statistical testing of the 3rd secondary endpoint in the multiple testing procedure described in section 4.1.3

Estimation of treatment effect

Win ratio:

For a summary statistic that uses the same ranking as that used in the hypothesis test, but has a clinical interpretation, the win ratio (WR) and the corresponding 95% confidence interval (Wang and Pocock 2016) will be reported. It is noted that the WR differs from the statistic used for hypothesis testing, so that exact consistency is not expected between these two analyses, e.g. on rare occasions, the confidence interval for WR could exclude unity while the pre-planned hypothesis test could be non-significant, or the hypothesis test could be

significant with the confidence interval for WR including unity. Formal inference for the superiority of the treatment over control will be made only from the preplanned hypothesis test.

The win ratio represents the odds of having a more favourable outcome versus a less favourable outcome when assigned to the dapagliflozin 10 mg treatment group as opposed to placebo. More specifically, each patient in the dapagliflozin group is compared with each patient in the placebo group and each pair is labelled as “winner”, “loser”, or “tie”, depending on whether the patient on dapagliflozin has a more favourable, less favourable, or the same outcome, respectively, with respect to the composite ranked endpoint compared to the patient on placebo. Win ratio is defined as the ratio of the number of “winner” pairs to the number of “loser” pairs for the dapagliflozin arm. If the estimated win ratio is greater than 1 then the treatment effect is estimated to be in favour of dapagliflozin.

The win ratio statistic adjusted for the randomization stratification factor and baseline TSS will be obtained using the methodology in

Koch et al 1998, Kawaguchi et al 2011 for the stratified Mann-Whitney estimators for the comparison of two treatments with randomization-based covariance adjustment. The win ratio statistic will be calculated as Mann-Whitney odds, i.e., $WR = MW / (1 - MW)$, where MW is the adjusted Mann-Whitney estimate. This transformation is monotonous in the domain of the Mann-Whitney estimate. The 95% confidence interval for the win ratio will be obtained by transforming the bounds of the confidence interval (

Koch et al 1998) for the Mann-Whitney estimate, using the same transformation as for the win ratio.

Responder analysis:

Number and percentage of patients in each treatment group will be summarized across the following categories:

5 point improvement from baseline to 8 months in TSS vs no significant improvement:

- Change from baseline in $TSS \geq 5$ points, vs
- Death prior to the 8 months assessment or change from baseline in $TSS < 5$ points.

5 point deterioration from baseline to 8 months in TSS vs no significant deterioration:

- Death prior to the 8 months assessment or change from baseline in $TSS \leq -5$ points, vs
- Change from baseline to 8 months in $TSS > -5$ points.

If a patient had a baseline value of $TSS \geq 95$ points, ie near the “ceiling”, they will be defined as having a 5 point improvement only if they had $TSS \geq 95$ points at 8 months. Similarly, if a patient had a baseline value of $TSS \leq 5$ points, ie near the “floor”, they will be defined as having a 5 point deterioration only if they had $TSS \leq 5$ points at 8 months.

The proportion of TSS responder categories will be compared between treatment groups using a logistic regression model including treatment group, stratification variable (T2D at randomisation) and baseline TSS value. The observed number of and proportion of TSS responders, odds ratio between treatment groups and its 95% confidence interval and corresponding 2-sided p-value estimated from each imputed dataset will be combined using Rubin's rule, and the combined results will be presented.

Additional responder analysis will be performed in the same way as for 5 points improvement and deterioration described above, using the thresholds of clinically meaningful within-patient change from baseline TSS derived from anchor-based analyses (10 point improvement, 10 point deterioration, 15 point improvement; Appendix B Section 8.2), with "ceiling" and "floor" values handled consistently.

Empirical cumulative distribution function (eCDF) plots will be presented by treatment group to summarize the distribution of change from baseline to 8 months in TSS values, where patients who die prior to the 8-month assessment will be represented with the value of -101 (a value below the worst possible change from baseline).

Handling of missing data

The number of patients with missing vital status at 8 months is expected to be negligible. If some patients are LTFU or patients who withdrew consent have unknown vital status, the main analysis will be done with these patients assigned the worst ranks (same as deaths).

In the context of analysing the composite ranked endpoint as described above, missing data may arise when patients miss the 8-month KCCQ assessment while remaining in the study during the 8-month assessment window, or when patients withdraw consent from the study prior to 8 months. If a patient is known to have died prior to the 8-month assessment, the patient is considered to have a non-missing composite outcome and will be handled as described above (assigned the worst rank). Otherwise, patients who are alive at 8 months and have missing baseline or 8-month KCCQ assessments will have their missing TSS imputed using the multiple imputation (MI) methodology as follows.

Missing TSS values at baseline or at 8 months will be imputed under the Missing at Random (MAR) assumption. The imputation will be done using a predictive mean matching multiple imputation model and a method of Fully Conditional Specification as implemented in the SAS Procedure MI (FCS statement). The predictive mean matching method ensures that the imputed values remain in the permissible range of the TSS values. The imputation model will include the treatment group, T2D randomization stratum, TSS at baseline, month 4, and 8, and a categorical variable representing the number of HF events (0, 1, ≥ 2 events) in the interval from randomization to 4 month and in the interval from 4 to 8 months. Occurrences of HF events will be determined based on the investigator-reported potential HF events. The auxiliary variable related to HF events is included in the imputation model to improve the imputation accuracy, because the occurrence of HF events is associated with quality of life assessed by KCCQ.

The number of closest observations used to sample an imputed value by the predictive mean matching method will be 5 (SAS default setting).

Each imputed dataset will be analysed using the methods described in the “Hypothesis testing” and “Estimation of treatment effect” sub-sections above. The results from multiple imputed datasets will be combined using Rubin’s rule as implemented in the SAS Procedure MIANALYZE.

- In the analysis of rank ANCOVA, the CMH test statistic used for the hypothesis test has a chi-square distribution. In order to apply Rubin’s combination rule, which assumes approximate normal distribution of the statistics being combined, a normalizing Wilson-Hilferty transformation will be applied to the CMH test statistics from each imputed dataset (Ratitch et al 2013). The standardized transformed statistic will be computed as follows:

$$st_{wh_cmh}^{(m)} = \frac{\sqrt[3]{\frac{cmh^{(m)}}{df} - \left(1 - \frac{2}{9 \times df}\right)}}{\sqrt[3]{\frac{2}{9 \times df}}}$$

where $cmh^{(m)}$ is the CMH statistic from the m^{th} imputed dataset and df is the number of degrees of freedom associated with the statistic (in this case equal to 1). The transformed statistics are approximately normally distributed with a mean of 0 and variance of 1 and can be combined using Rubin’s rule.

- For the estimation of the win ratio, a combined Mann-Whitney estimate (MW) and its standard error ($SE(MW)$) will first be obtained by applying Rubin’s rule to the corresponding estimates from multiple imputed datasets. Then the win ratio and its 95% confidence interval will be obtained based on the combined Mann-Whitney estimate and its standard error as previously described.
- For the summaries of number and percentage of subjects in the categories of significant improvement and deterioration from baseline, as discussed in the “Estimation of treatment effect” sub-section above, the average number and percent of subjects in each category across all multiple imputed datasets will be reported. The TSS responder analyses will use the imputation datasets created for the main analysis. Therefore, deaths will be defined as non-responders, and responder status will be determined based on the imputed TSS values for the patients who have missing TSS due to reasons other than death.

Supportive analyses and sensitivity analyses

The number and percent of patients who die prior to the 8-month assessment will be summarized by treatment group.

Descriptive statistics of scores and change from baseline at 4, and 8 months will be presented for total symptom score, overall summary score, clinical summary score and domains (Physical limitation, symptom stability, symptom frequency, symptom burden, quality of life, self-efficacy and social limitation).

The testing and estimation described for change from baseline at 8 months in TSS, will be repeated in an exploratory fashion for change from baseline in TSS at 4 months, and for the overall summary score and clinical summary scores at 4 and 8 months.

To assess the impact on TSS change from baseline of a treatment effect on mortality, an alternative ranking will be applied, where patients deceased prior to the 8-month assessment will be assigned the same worst rank regardless of their last value while alive. This is done to reduce the impact of treatment differences in time to CV death on the assessment of this KCCQ secondary endpoint.

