3.2 Secondary variables

The secondary endpoints are included in a hierarchical testing sequence following the primary endpoint as ordered in Section 3.2.1 - 3.2.5.

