3.2.2 Total number of (first and recurrent) hospitalizations for HF and CV death

The efficacy variable is the total number of first and recurrent hospitalizations for HF and CV death, not including urgent HF visit.

For the analysis of recurrent heart failure hospitalization and CV death, the data will be expressed in counting process style for input to the analysis as described in Section 4.2.4.1. The time from randomization to end of follow-up/censoring will be split into one or more interval with variables for start of interval, end of interval and a variable indicating if an event occurred at the end of each respective interval, or if the patient was censored. Recurrent HF hospitalizations, CV death and censoring processes all have continuous distributions so that HF hospitalization and death cannot happen at the same time. If HF hospitalization and CV death occurred at the same day, then only the CV death will be counted.

Patients who did not have the endpoint will be censored by the same rule as for the primary endpoint.

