4. ANALYSIS METHODS

4.1 General principles

No multiplicity adjustment will be made to confidence intervals as they will be interpreted descriptively and used as a measure of precision. All p-values will be unadjusted. P-values for variables not included in the confirmatory testing sequence, or following a non-significant test in the sequence will be regarded as nominal.

The primary and secondary analyses include adjudicated events occurring on or prior to PACD.

Stratification of analyses for T2D status will be performed using the stratification values as entered in IxRS to determine the randomization assignment.

Baseline diabetic status

T2D at baseline will be defined as established diagnosis of T2D (recorded in eCRF medical history) or central laboratory HbA1c $\geq 6.5\%$ at both visit 1 (enrollment) and visit 2 (randomisation).

Exploratory analyses may include “pre-diabetic” subjects not categorized as T2D above and having central laboratory HbA1c $\geq 5.7\%$ at visit 1 and/or visit 2. Other subjects will be categorized to a third group, here denoted “normo-glycaemic”

In consideration of missing data, subjects without medical history of T2D and a single HbA1c $\geq 5.7\%$ (including $\geq 6.5\%$) from visit 1 or visit 2 will be categorized as pre-diabetic. Subjects without medical history of T2D and no HbA1c measurement or a single measurement $< 5.7\%$ will be included in the normo-glycaemic group (thus non-diabetic).

Incomplete dates

All efforts should be made to obtain complete dates of clinical assessments and events. For analyses requiring complete dates, partially missing dates will be imputed based on available corroborating information. Absent of any additional corroborating information, partially missing dates will be imputed as follows: if only the year part of a date is available (YY), then the date will be set to YY0701. If only the year and month is available (YYMM), then the date will be set to YYMM15. Additional imputation rules will be defined as appropriate to ensure that eg, dates will not be imputed as prior to randomization, after death or end date before start date.

Baseline laboratory value

For all laboratory variables, with the exception of eGFR, the baseline value is defined as the last value on or prior to date of first dose of randomized study drug, or for patients who did not receive treatment, the last value on or prior to date of randomization.

eGFR

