4.1.3 Confirmatory testing procedure

A closed testing procedure including a pre-specified hierarchical order of the primary and secondary endpoints will be utilized. The Type I error will be controlled at a one-sided 0.02496 level for multiplicity across primary and secondary endpoints and in consideration of the planned interim analysis. Statistical significance will be assessed in the pre-specified order of the endpoints as specified in Section 1.1.1 and 1.1.2. The testing procedure will continue down the hierarchy if the preceding endpoint is rejected at a one-sided 0.02496 level and will stop if the null hypothesis for the preceding endpoint is not rejected at a one-sided 0.02496 level.

If the study is stopped in the efficacy interim analysis (Section 5), testing of secondary endpoints will continue down the hierarchy at one-sided significance level 0.001.

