4.2.3 Analysis of the primary efficacy variable

The primary variable is the time to first event included in the primary composite endpoint. The primary analysis will be based on the ITT principle using the FAS, including events with onset on or prior to PACD, adjudicated and confirmed by the CEA committee.

In the analysis of the primary composite endpoint, treatments (dapagliflozin versus placebo) will be compared using a Cox proportional hazards model with a factor for treatment group, stratified by T2D status at randomization, and adjusting for history of hospitalization for heart failure. The analysis will use WoC, non-CV death, last clinical event assessment and PACD for censoring of patients without any primary event as described in Section 3.1. The Efron method for ties and p-value based on the score statistic will be used. The event rates, p-value, HR, and 95% confidence interval will be reported.

The contribution of each component of the primary composite endpoint to the overall treatment effect will be examined. In the analysis of the components, all first event of the given type will be included irrespective of any preceding non-fatal composite event of a different type. Consequently, the sum of the number of patients with events in the component analysis will be larger than the number of patients with composite events. Methods similar to those described for the primary analysis will be used to separately analyze the time from randomization to the first occurrence of each component of the primary composite endpoint.

Kaplan-Meier estimates of the cumulative proportion of patients with event will be calculated and plotted, for the composite endpoint and for the individual components.

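### Does the confirmatory LWYY test in SAP section 4.2.4.1 need its stratum and covariate written down before it can be relied on?

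*SAP*

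**What the plan says.** Section 3.2 makes the endpoint confirmatory: "The secondary endpoints are included in a hierarchical testing sequence following the primary endpoint as ordered in Section 3.2.1 - 3.2.5". Recurrent HF hospitalizations and CV death are section 3.2.2, the second secondary endpoint. Under section 4.1.3, testing "will stop if the null hypothesis for the preceding endpoint is not rejected at a one-sided 0.02496 level".

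Section 3.2.2 covers data layout and censoring only, and passes the model on: "the data will be expressed in counting process style for input to the analysis as described in Section 4.2.4.1". Section 4.2.4.1 then gives the method "known as the LWYY (Lin-Wei-Yang-Ying) method, to test the treatment effect and to quantify the treatment difference", the output (rate ratio, 95% confidence interval, p-value) and the rule for an HF hospitalization and CV death on the same day. It lists no model terms.

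Other sections do name terms:
- Primary Cox model, section 4.2.3: "stratified by T2D status at randomization, and adjusting for history of hospitalization for heart failure".
- First CV death or HF hospitalization, section 4.2.4: stratified by T2D, and "The composite of hospitalization for HF or CV death will be adjusted for history of hospitalization for heart failure".
- Both hazards of the joint frailty model, section 4.2.4.1: "stratified by T2D status at randomization with treatment and history of hospitalization for heart failure as covariates".

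Section 4.1 adds a general rule: "Stratification of analyses for T2D status will be performed using the stratification values as entered in IxRS to determine the randomization assignment".

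**The concern.** A confirmatory test should have one p-value fixed in advance. Here the text permits two readings: a model with treatment alone, which is the literal one, or a model with the same stratum and covariate as its neighbours. The two can fall on opposite sides of the one-sided 0.02496 limit. A failure would close the hierarchy for KCCQ, the renal composite and all-cause death. The supportive frailty models are specified down to the baseline hazard and the frailty distribution, while the test that carries alpha is given by method name only. If the literal reading were followed, some efficiency might also be lost by ignoring two prognostic factors.

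**Working it through.** **1. Is the gap real?** The six confirmatory tests side by side:

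| Test | SAP section | T2D stratum stated | Covariate stated |
|---|---|---|---|
| Primary composite | 4.2.3 | yes | prior HF hospitalization |
| First CV death/HF hospitalization | 4.2.4 | yes | prior HF hospitalization |
| Recurrent HF hospitalization and CV death (LWYY) | 4.2.4.1 | no | none |
| KCCQ total symptom score | 4.2.4.2 | yes | baseline score |
| Renal composite | 4.2.4 | yes | baseline eGFR |
| All-cause death | 4.2.4 | yes | none named separately |

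The sentence in 4.2.4 that carries over the primary method follows a list of three time-to-event variables, and the recurrent-event endpoint is not among them. The frailty terms in 4.2.4.1 are assumptions of the component analyses. Section 4.1 fixes the source of the T2D values. Read generously it supplies the stratum, but never the covariate. So the gap is real.

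**2. The plan's own figures.** The SAP gives no power figure for LWYY, so only the design inputs can be reproduced. With hazard ratio 0.80, one-sided 2.5%, 90% power and 1:1 allocation (section 1.4), events = 4(1.960 + 1.282)²/(ln 0.80)² ≈ 844.1. This rounds up to 845 against the stated 844, and 844 events give 89.997% power. With an interim at 75% and one-sided 0.001, a bivariate normal with correlation √0.75 leaves 0.02496 for the final analysis, as stated.

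**3. Treatment-only against stratified and adjusted LWYY.** Both were fitted by partial likelihood with a patient-clustered sandwich variance, 3000 simulated trials per scenario.
- From the SAP: 4500 patients, 1:1 allocation, 18 months' accrual in a 33-month study (follow-up 15 to 33 months), ratio 0.80, one-sided 0.02496, and a placebo first-event rate of 11 per 100 patient-years. That rate is the primary-composite figure, applied here to HF hospitalization or CV death.
- Assumed: T2D 43%, prior HF hospitalization 50%, gamma frailty variance 1.5 or 3, CV death 40% (one run 25%) of event intensity, and the prognostic ratios shown.

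| Prognostic ratios, T2D/prior hospitalization | Frailty variance | Variance ratio, adjusted to unadjusted | Power %, unadjusted to adjusted | Opposite verdicts |
|---|---|---|---|---|
| 1.0/1.0 | 1.5 | 1.000 | 83.5 to 83.7 | 0.3% |
| 1.3/1.5 | 1.5 | 0.995 | 82.9 to 82.9 | 1.7% |
| 1.3/1.5 | 3 | 0.996 | 72.4 to 72.5 | 1.9% |
| 1.6/2.5 | 1.5 | 0.979 | 78.5 to 79.8 | 3.6% |
| 1.6/2.5 | 3 | 0.985 | 71.2 to 72.6 | 4.6% |
| 1.6/2.5, CV death 25% | 1.5 | 0.972 | 81.4 to 83.3 | 4.5% |

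At a true ratio of 0.87 (frailty 1.5), power is 44.9 to 45.1 with 2.9% opposite verdicts (1.3/1.5), and 42.6 to 44.1 with 6.1% (1.6/2.5). Under the null, rejection is 2.4% treatment-only and 2.4 to 2.6% adjusted. Mean rate ratios agree within 0.002. The Monte Carlo standard error of the power differences is 0.1 to 0.45 points.

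**4. Second check, separate code and assumptions.** T2D 45%, prior hospitalization 45%, frailty variance 1.5, ratio 0.83, 1200 trials each. With prognostic ratios 1.4 (T2D) and 1.5 (prior hospitalization), power is 71.4% for both fits, with 2.7% opposite verdicts. With 1.5 and 2.0, power is 70.0% against 71.2%, with 4.8% opposite verdicts.

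A hand formula agrees: opposite verdicts ≈ φ(z for the power) × 0.798 × SD of the difference between the two z-statistics.
- Weaker: φ(0.565) × 0.798 × 0.115 = 0.340 × 0.0918 = 3.1%.
- Stronger: φ(0.524) × 0.798 × 0.166 = 0.348 × 0.1325 = 4.6%.

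**5. Worst case: the better fit picked after unblinding.** Under the null (1600 trials each), P(either rejects) = ½ × (reject unadjusted + reject adjusted + opposite verdicts).
- Weaker: ½(2.375 + 2.3125 + 0.4375) = 2.56%.
- Stronger: ½(2.4375 + 2.625 + 1.0625) = 3.06%.

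The Monte Carlo standard error is about √(0.025 × 0.975/1600) = 0.4 points.

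**The case for a change.** The best case for a change is that an inference is not pre-specification. Five of the six confirmatory tests have their stratum written down and this one does not. The section that should hold the terms is the one to which 3.2.2 sends the reader. The test gates three others, the choice can alter the verdict in a few percent of trials, and one sentence would settle it.

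The textual part stands: nothing in the SAP supplies the covariate. The rest carries less weight. The two harms exclude each other. If the text is read literally, the model is fixed and valid, and only a small efficiency preference remains. If the choice is open, no efficiency loss has been shown. Opposite verdicts go in both directions, so neither reading favours a claim of benefit, and rising above the nominal level would require choosing after unblinding. The plan also varies covariates by endpoint, so a difference from the neighbouring models is not in itself a contradiction.

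Nor does a rival p-value exist. Section 4.2.4.1 assigns the test to LWYY and the frailty model to the components, and a robust patient-level variance belongs to the named method. Finally, SAP section 6 lists the KCCQ analysis as the only departure from the protocol, so any LWYY terms given there would still apply. The protocol is not at hand, so this point cannot be confirmed.

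**Conclusion.** No change is needed. Section 4.2.4.1 leaves out the stratum and covariate of the LWYY model, but it states nothing wrong and contradicts nothing. An analyst would very likely use the IxRS T2D stratum and prior HF hospitalization, as the neighbouring HF models do. One who fitted treatment alone would still have a sound test. The power difference is 0 to 0.1 points under moderate prognostic ratios (1.3/1.5) and at most 1.9 points under strong ones (1.6/2.5). Each fit alone holds its level, at about 2.3 to 2.6%.

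These sizes rest on assumed T2D and prior-hospitalization prevalences, frailty variance, CV-death share and prognostic ratios, none of which the SAP gives, so they show order of magnitude only. The conclusion also assumes that the model is programmed before unblinding. Choosing between fits afterwards could bring the one-sided error to about 2.6 to 3.1%.
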